#### **Secondary outcomes analysis**

The following secondary outcomes will be considered:

- Rate of response at follow up visit-achievement of remission (CDAI≤2.8) in patients with LDA, moderate, or high disease activity (CDAI>2.8) at baseline. Patients who discontinue tofa within 6 months and switch to another biologic or JAK will be considered “non-responders”.
- Mean of change in CDAI from baseline to follow up visit (6/12). Change in CDAI will be calculated by subtracting baseline CDAI from CDAI measured at 6 months. If a patient discontinues tofa but does not switch to another biologic, the CDAI value at follow up visit (6/12) will be used. If a patient discontinues tofa and switches to another biologic or JAK, the CDAI value at the switch visit will be used for change in CDAI calculation.
- HAQ (HAQ):  
Mean change of HAQ from index date to follow-up visit

- Patient pain (0-100 VAS scale):  
Mean change in pain from index date to follow-up visit
- Patient fatigue (0-100 VAS scale):  
Mean change in fatigue from index date to follow-up visit
- Achievement of modified ACR (mACR)20, mACR50, mACR70
- Achievement of LDA or remission defined by DAS28(ESR) ( $\leq 3.2$ ) in those patients who have DAS28 $>3.2$  at the initiation visit
- Achievement of “mild pain”, defined as  $\leq 20$ mm on 100 VAS scale in those patients who have pain  $>20$  mm on 100 VAS at the initiation visit

Mean changes, rates of response, and corresponding 95% confidence intervals will be reported in total and in each group [Table 5].

Two sets of analyses will be report based on patient with 6 month follow up and patients with 12 months follow up.

All statistical analyses will be performed using STATA Version 15.1 (StataCorp, LLC, College Station, TX).

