### **2.5.2. Effectiveness Analysis**

#### **Primary outcome analyses**

We will estimate the rate of response at 6 and 12 months. Response is defined as the achievement of LDA (CDAI≤10) in patients with moderate or high disease activity (CDAI>10) at baseline. Patients who discontinue tofa within 6 (or 12) months and switch to another biologic or JAK will be considered “non-responders”. Effectiveness outcomes at the 6- and 12- month visits will be estimated in overall tofa initiators and by groups for each milestone. We will report the rate of response and 95% CI for the proportion of response, for patients overall and for each group in [table 5](#).

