# of discontinuations			
# of patients reporting at least one reason			
Total # of reasons			
Safety			
Efficacy			
Cost/Insurance			
Other reason			

Notes:

- Side effect: includes infection, lymphoma/malignancy, toxicity, serious and minor side effect;
- Efficacy: includes lack of efficacy, disease flare, active disease, primary loss of efficacy, and secondary loss of efficacy, inadequate initial response, failure to maintain initial response;
- Cost/Insurance: includes lack of insurance
- Other reason: includes no longer needed, formulary restriction, patient preference, recent journal report, recent meeting report, withdrawn by FDA, physician preference, peer suggestion, fear of future side effect, patient doing well, and frequency of administration, temporary interruption, to improve compliance, to improve tolerability, route of administration.

Table 5. Outcome measures at 6 months after tofa initiation, overall and for monotherapy and combination therapy groups

Binary outcomes n(%) 95% CI	All Tofa Initiators N=	Tofa Monotherapy N=	Tofa Combo therapy N=
	n=	n=	n=
LDA (CDAI≤10) a			
	n=	n=	n=
Remission (CDAI≤2.8) b			
mACR20			
mACR50			
mACR70			
	n=	n=	n=
DAS28(ESR)≤3.2 c			
	n=	n=	n=
Achievement of “mild pain” (≤ 20mm on 100 VAS) d			
Continue outcomes: Mean (SD) 95% CI			
Δ CDAI:			
Δ patient global			
Δ HAQ			
Δ patient pain			
Δ patient fatigue			

a Calculated among those patients with moderate or high disease activity (CDAI>10) at baseline.

b Calculated among those patients with LDA, moderate or high disease activity (CDAI>2.8) at baseline.

c Calculated among those patients who have DAS28>3.2 at the initiation visit

d Calculated among those patients who have pain >20 mm on 100 VAS at the initiation visit

Tables 6-10 will repeat tables 1-5, by line of therapy (2nd line, 3rd line, and 4th line) for Milestone 2.

Table 11-15 will repeat table 1-5, by tofa dose (5mg/bid and 11mg/qd) for Milestone 3.

Table 16-20 will repeat table 1-5 for the three time periods of initiation (2012-2014, 2015-2017, 2018-2020) for milestone 4.

Table 21-40 will repeat tables 1-20 for patients with 12 months follow up by 4 milestone.

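### The CDAI remission rule fails switchers only up to month 6, although remission is also reported at 12 months and the LDA rule runs to month 12

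*SAP*

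**What the plan says.** All of this is in SAP section 2.5.2 and the shell tables of SAP section 3.

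- **LDA (primary).** "Patients who discontinue tofa within 6 (or 12) months and switch to another biologic or JAK will be considered" non-responders. The window follows the time point.
- **CDAI remission (secondary).** "Patients who discontinue tofa within 6 months and switch to another biologic or JAK will be considered" non-responders. The same bullet defines the outcome at the follow-up visit, not at month 6 alone.
- **Change in CDAI (secondary).** The bullet is labelled for both visits, but then: "Change in CDAI will be calculated by subtracting baseline CDAI from CDAI measured at 6 months". Switchers contribute the CDAI recorded at the switch visit.
- **Both time points are planned.** "Two sets of analyses will be report based on patient with 6 month follow up and patients with 12 months follow up". In section 3: "Table 21-40 will repeat tables 1-20 for patients with 12 months follow up by 4 milestone". Table 5, with its remission row, is therefore produced again for the 12-month cohort.
- **Other Table 5 rows.** "Achievement of modified ACR (mACR)20, mACR50, mACR70", DAS28(ESR) ≤3.2 and mild pain carry no instruction on switchers. A change in "patient global" row appears only in the table shell. For HAQ the SAP gives "Mean change of HAQ from index date to follow-up visit", and pain and fatigue are worded in the same way.

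**The concern.** Objectives 2 and 3 estimate tofacitinib effectiveness at 6 and 12 months. A patient who leaves tofacitinib for another biologic or JAK inhibitor and then does well has responded to the next drug. The SAP recognises this for LDA at both time points, but for remission only up to month 6. Patients who switch between months 6 and 12 fall into the gap.

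Two things are at stake. First, CDAI ≤2.8 implies CDAI ≤10, so remission should be nested within LDA among patients who start above 10. The literal rules break that nesting. Second, 12-month remission can include responses reached on another drug.

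**Working it through.** **1. The rules side by side**

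| Table 5 row | Switcher handling at 6 months | Switcher handling at 12 months |
|---|---|---|
| LDA | non-responder if stopped within 6 months and switched | non-responder if stopped within 12 months and switched |
| Remission | non-responder if stopped within 6 months and switched | same 6-month limit; nothing for months 6-12 |
| Change in CDAI | switch-visit value | switch-visit value, though the calculation sentence names only month 6 |
| mACR20/50/70, DAS28(ESR) ≤3.2, mild pain, change in patient global | none stated | none stated |
| Change in HAQ, pain, fatigue | follow-up visit value | follow-up visit value |

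Nothing in either document gives a reason for a shorter remission window. The change-in-CDAI bullet has the same 6-month-only wording under a label covering both visits, which points to a drafting slip.

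**2. A patient who exposes the conflict**

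Baseline CDAI is above 10, so the patient is in both denominators. The switch is at month 8. The next visit, six months later at month 14, lies in the 10-15 month window of SAP section 2.4.5, and CDAI there is 2.

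- LDA at 12 months: stopped within 12 months and switched, so non-responder.
- Remission at 12 months: did not stop within 6 months, so the rule does not apply; 2 ≤ 2.8, so responder.

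**3. Illustrative size**

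The documents contain no figure to reproduce here. From the documents: 1223 patients with 12-month follow-up (SAP 2.4.4), selection of the visit closest to 12 months within 10-15 (SAP 2.4.5), and a registry visit when a new eligible drug is prescribed or first given at a routine office visit (Protocol 9.4). Assumed: 15-30% switch by month 12 with exponential switch times; visits otherwise six months after the previous one with SD 0, 1 or 2 months; and a share *r* = 5-25% of those scored on the next drug who are in remission.

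Let *s* be the share of patients with a 12-month visit who switch after month 6 and before that selected visit. It was simulated with 400,000 patients in each of 12 settings. The shift in the remission proportion is *s* × *r*.

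| Visits at switch | *s* | *r* = 5%, lowest *s* | *r* = 15% | *r* = 25%, highest *s* |
|---|---|---|---|---|
| every switch | 3.75-8.05% | 0.05 × 0.0375 = 0.2 points | 0.6-1.2 points | 0.25 × 0.0805 = 2.0 points |
| half of switches | 5.5-11.2% | 0.05 × 0.055 = 0.3 points | 0.8-1.7 points | 0.25 × 0.112 = 2.8 points |

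In patients, with a visit at every switch: 1223 × 0.0375 = 46 to 1223 × 0.0805 = 98 are scored on the next drug. At *r* = 15% that is 7-15 patients misclassified. The 1223 is the whole 12-month cohort; the remission denominator (baseline CDAI above 2.8) is smaller and not given.

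For scale, the 95% CI half-width at 15% remission is 1.96 × √(0.15 × 0.85 / 1223) = 2.0 points.

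Looser inputs widen the range: *s* = 5-20% and *r* = 5-30% give 0.25-6.0 points. The top of that range needs a larger *s* than either row of the table produces.

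**4. What remains after extending the window to 12 months**

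Patients who switch after month 12 but before their selected visit would still be scored on the next drug: none with a visit at every switch, and 0-0.9% with visits at half of them.

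**The case against.** The strongest reply is that this is a slip whose intent can be read from the LDA rule and from the label of the next bullet. Remission is a secondary outcome in a descriptive study without hypotheses, and at *r* = 15% the shift is below the CI half-width. Most of that stands: the matter is mainly one of coherence, and the size is modest under the assumptions shown. But the literal text can be programmed as it is and gives a different 12-month figure from the inferred one, so the SAP should not leave it to inference.

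A reader might go further and infer that the nine Table 5 rows outside the CDAI outcomes are also wrong, and that one switcher rule must be imposed on all twelve. The documents do not support that. HAQ, pain and fatigue have a stated value, the one at the follow-up visit, and observed values regardless of switching can be a valid choice. Nothing requires a uniform rule. Imposing the switch-visit value would also be debatable: inclusion guarantees only CDAI, so other measures may be missing at that visit, and SAP section 2.5 itself allows for drugs started between visits. What survives is narrower. The LDA rule cannot be presumed to cover mACR, DAS28 and mild pain, because it sits under the primary outcome and is restated separately for remission. The handling in those rows, and for change in patient global, is simply not stated.

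A reader might also infer that 12-month remission is materially inflated or that the primary result is affected. The first cannot be known without switch and response rates. The second is not so, because the LDA rule already covers both windows.

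**Conclusion.** The remission rule is wrong as written. Its 6-month limit conflicts with the reporting of remission at 12 months and with the LDA rule, and it allows a patient to be in remission without being in LDA. This follows from the text alone and needs no assumption.

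The size is unknown. Under the assumed rates it is about 0.2-2 points on 12-month remission with a visit at every switch, and up to about 3 points with visits at half of them; these figures are illustrative only. The 6-month remission rule and the primary LDA outcome are unaffected.

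The unstated handling in the other rows is a secondary matter of clarity, not an error in those outcomes. It is worth correcting the SAP before the 12-month tables are produced.

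**What to change.** 1. In the remission bullet, replace the 6-month limit with 6 (or 12) months, as in the LDA rule.
2. In the change-in-CDAI bullet, refer to CDAI measured at 6 (or 12) months.
3. Add a program check: at each time point, no patient with baseline CDAI above 10 may be a remission responder and an LDA non-responder.
4. State the switcher handling used for each Table 5 row, and label rows that include values measured after a switch. No single rule need be prescribed.

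Items 1-3 cost a few words and one line of checking; switch dates are already needed for LDA. Item 4 adds a sentence per row or group of rows and a footnote to Table 5 and its repeats (Tables 5, 10, 15, 20, 25, 30, 35 and 40). The LDA rule is unchanged, so the condition for a protocol amendment in Protocol section 9.7 is not met.

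The downside is that 12-month remission becomes equal or slightly lower. Besides removing responses reached on the next drug, the extended rule also fails patients whose selected visit is the switch visit itself, as the LDA rule already does. Under the same assumptions, with a visit at every switch, these are 2.4-5.2% of patients; if 0-15% of them are in remission at that visit, the cost is at most 0.15 × 0.052 = 0.8 points.

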### 3. Shell Tables

Milestone 1: Results for tofa monotherapy and combination therapy

Milestone 2: Results for line of therapy (2nd, 3rd, 4th line)

Milestone 3: Results for tofa dose (5mg and 11mg)

Milestone 4: Results for tofa initiation time periods (2012-2014, 2015-2017, and 2018-2020)

Table 1. Demographic and clinical characteristics at tofa initiation visit, overall and for monotherapy and combination therapy in patients with 6 months follow up.

	All Patients	Tofa monotherapy	Tofa combination therapy ‡	P-value*
	N=	N=	N=	
Demographic/socioeconomic characteristics				
Age: Mean±SD				
Median (IQR)				
Female: n(%)				
Race/Ethnicity: n(%)				
White				
Hispanic				
Black				
Asian				
Other				
Type of Insurance:				
None: n (%)				
Private: n (%)				
Medicare: n (%)				
Medicaid: n (%)				
Final education: n(%)				
Primary				
High school				
College/Univ.				
Unknown				
Work Status: n(%)				
Full Time				
Part Time				
Disabled				

Retired				
Other				
Lifestyle				
Smoking status: n(%)				
Never				
Previous				
Current				
Weight (lb): Mean±SD				
Median (IQR)				
BMI: Mean±SD				
Median (IQR)				
History of comorbidities: n(%)				
Cardiovascular disease**				
Malignancy***				
Hypertension				
Diabetes				
Osteoporosis				
Fibromyalgia				
Depression				

\* T-tests will be used to evaluate mean differences between groups for continuous variables, and Chi-square tests will be used to evaluate differences between treatment groups for categorical variables

\*\* included: MI, stroke, TIA acute coronary syndrome, coronary artery disease, CHF, revascularization procedure including percutaneous coronary intervention [PCI], coronary artery bypass grafting [CABG] or coronary artery stents, ventricular arrhythmia, cardiac arrest, unstable angina, other CVs, carotid artery disease.

\*\*\* History of lung cancer, breast cancer, lymphoma, skin cancer (melanoma and squamous), and other cancer

‡ Combination therapy refers to tofa+MTX, arava, azulfidine, plaquenil, or cyclosporine

Table 2. RA disease characteristics, disease activity measures and PROs at tofa initiation visit, overall and for monotherapy and combination therapy in patients with 6 months follow up.

	All Patients	Tofa Monotherapy	Tofa Combination Therapy ‡	P value*
	N=	N=	N=	
RA disease characteristics				
Duration of RA: Mean±SD				
Median (IQR)				
Age onset RA: Mean±SD				
Median (IQR)				
Disease Activities				
CDAI: Mean±SD				
Median (IQR)				
Category of disease activity: n(%)				
Remission				
LDA				
MDA				
HAD				
Tender Joint Count (28): Mean±SD				
Median (IQR)				
Swollen Joint Count (28): Mean±SD				
Median (IQR)				
Physician Global Assessment(0-100):				
Mean±SD				
Median (IQR)				
DAS28(ESR): Mean±SD				
Median (IQR)				
Patient reported outcomes				
Patient Global Assessment: Mean±SD				
Median (IQR)				
Patient Pain Assessment: Mean±SD				
Median (IQR)				
Patient Fatigue Assessment: Mean±SD				
Median (IQR)				
HAQ (0-3): Mean±SD				
Median (IQR)				
mHAQ: Mean±SD				
Median (IQR)				
Morning Stiffness: n(%)				

Stiffness(mins): Mean±SD**			
Median (IQR)			
Treatment			
Concomitant therapies: n(%)			
None			
MTX only			
nonMTX csDMARD only			
MTX & nonMTX csDMARD			
History of csDMARD: n(%)			
None			
1			
2+			
History of biologics: n(%)			
None			
1			
2+			
Prednisone			
History of prednisone use: n(%)			
Current prednisone use: n(%)			
Dose in users: Mean±SD			
Median (IQR)			
Mode of Action (MOA) History			
Immediately previous treatment			
TNF inhibitor			
Non-TNF inhibitor			
csDMARDs			
tsDMARDs			
History of treatment of MOA (Ever)			
TNF inhibitor			
Non-TNF inhibitor			
csDMARDs			
tsDMARDs			

\* T-tests will be used to evaluate mean differences between groups for continuous variables, and Chi-square tests will be used to evaluate differences between categorical variables

\*\* in patients reported morning stiffness

† Combination therapy refers to tofa+MTX, arava, azulfidine, plaquenil, or cyclosporine

Table 3. Reasons for initiation of tofacitinib in patients with 6 month follow up

n(%)	All Tofa	Tofa mono	Tofa combo
	N=	N=	N=
# of initiations			
# of patients reporting at least one reason			
Total # of reasons			
Safety			
Efficacy			
Cost/Insurance			
Other reason			

Table 4. Reasons for discontinuation of tofacitinib in 6 months

n(%)	All	Tofa mono	Tofa combo
	N=	N=	N=
# of discontinuations			
# of patients reporting at least one reason			
Total # of reasons			
Safety			
Efficacy			
Cost/Insurance			
Other reason			

Notes:

- Side effect: includes infection, lymphoma/malignancy, toxicity, serious and minor side effect;
- Efficacy: includes lack of efficacy, disease flare, active disease, primary loss of efficacy, and secondary loss of efficacy, inadequate initial response, failure to maintain initial response;
- Cost/Insurance: includes lack of insurance
- Other reason: includes no longer needed, formulary restriction, patient preference, recent journal report, recent meeting report, withdrawn by FDA, physician preference, peer suggestion, fear of future side effect, patient doing well, and frequency of administration, temporary interruption, to improve compliance, to improve tolerability, route of administration.

Table 5. Outcome measures at 6 months after tofa initiation, overall and for monotherapy and combination therapy groups

Binary outcomes n(%) 95% CI	All Tofa Initiators N=	Tofa Monotherapy N=	Tofa Combo therapy N=
	n=	n=	n=
LDA (CDAI≤10) a			
	n=	n=	n=
Remission (CDAI≤2.8) b			
mACR20			
mACR50			
mACR70			
	n=	n=	n=
DAS28(ESR)≤3.2 c			
	n=	n=	n=
Achievement of “mild pain” (≤ 20mm on 100 VAS) d			
Continue outcomes: Mean (SD) 95% CI			
Δ CDAI:			
Δ patient global			
Δ HAQ			
Δ patient pain			
Δ patient fatigue			

a Calculated among those patients with moderate or high disease activity (CDAI>10) at baseline.

b Calculated among those patients with LDA, moderate or high disease activity (CDAI>2.8) at baseline.

c Calculated among those patients who have DAS28>3.2 at the initiation visit

d Calculated among those patients who have pain >20 mm on 100 VAS at the initiation visit

Tables 6-10 will repeat tables 1-5, by line of therapy (2nd line, 3rd line, and 4th line) for Milestone 2.

Table 11-15 will repeat table 1-5, by tofa dose (5mg/bid and 11mg/qd) for Milestone 3.

Table 16-20 will repeat table 1-5 for the three time periods of initiation (2012-2014, 2015-2017, 2018-2020) for milestone 4.

Table 21-40 will repeat tables 1-20 for patients with 12 months follow up by 4 milestone.

